c. Remote screening visit alternative. Patients may also complete the initial visit remotely if warranted. In this case, subjects will be electronically consented through a secure platform such as Doxy.me or Redcap. The informed consent will be emailed to the participant prior to the video call. The patient will have the opportunity to ask questions on the call and will electronically sign the document. A signed copy will be emailed to the participant. The M.I.N.I interview and medical history then be conducted, also via Doxy.me. If clinically indicated, patients may have a physical exam the UDS visit. To date, no patients have been excluded due to physical exam findings. Patients will be advised to find a private location during these procedures to protect privacy and confidentiality. Patients will be sent survey links to complete self-report questionnaires.

d. Blood draws: In order to investigate the impact of moderate to heavy cannabis use and menstrual cycle on the endocannabinoid system, blood will be taken at Days 1, 8 and 22.

C.2.c.3. Progesterone Administration Procedures (Study Days 1-7). Following completion of screening procedures, participants will be scheduled to come to the clinic for training on CREMA and saliva (progesterone) collection procedures. The TLFB calendar will be completed. For female participants, menstrual history data will be used to schedule this session in the early follicular phase to standardize progesterone (or placebo) administration. During the early follicular phase, defined as the first 7 days after the onset of menses, ovarian hormones are low and largely invariant (approximately <1.1 ng/ml for progesterone and <85 pg/ml for estradiol; Chabbert-Buffet et al., 1998). This is critical for two reasons; first, to minimize the interaction between endogenous and exogenous sex hormones, and second, to achieve consistency between males and females as progesterone levels in men are steady and similar to levels observed in women during most of the follicular phase (Zumoff et al., 1990). At this visit, a urine sample will be collected to assess baseline cannabinoid level for purposes of cannabis abstinence verification (described below). Participants will be instructed to refrain from cannabis use during this study period.

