Participants will be provided with a seven-day supply of progesterone or placebo. Randomization to treatment will be done by the MUSC Investigational Drug Service (IDS). Dosing will begin in the evening on study day 1. On study days 2-7 participants will take medication at home in the morning and evening, and on day 8 the final dose will be taken at in the morning prior to completion of the laboratory stress task (described below). Progesterone and matching placebo capsules will be prepared and dispensed by the MUSC IDS. Previous studies (Fox et al., 2013; Sofuoglu et al., 2001; 2011) have used twice daily administration of 200mg progesterone during the early follicular phase to achieve stable levels of progesterone comparable to normal luteal phase levels (2-20 ng/ml). Safety and tolerability of micronized progesterone have been established in numerous studies with nicotine (Sofuoglu et al., 2001; 2011) and cocaine (Evans & Foltin, 2006; Fox et al., 2013; Reed et al., 2011 Sofuoglu et al., 2002; 2004) dependent individuals.

c. Cannabis Abstinence Verification. Cannabis abstinence will be assessed using self-report, saliva drug testing, and cannabinoid levels. Self-report will be collected at study visits using the TLFB as well as collected daily through mobile surveys or “morning reports” completed via mobile electronic device. Participants will be trained to self-administer saliva drug screening (Oratect FDA approved saliva test.). This test is able to detect THC in saliva for up to 14 hours. Participants will be instructed to complete two saliva drug tests daily using the RedCap video upload procedure described below under *Medication Adherence/Drug Test Monitoring*. A test will be completed in the office on Day 1 so patients can practice the procedure. Cannabinoid levels will also be assessed using urine toxicology collected on Study Days 8 and 22. Creatinine-corrected cannabinoid levels will be compared from Day 1 to Day 8 to confirm abstinence during the study period. Our group has recently published on the need for utilization of multiple methods to determine cannabis abstinence (Baker et al., in press). Contingency management (monetary compensation) procedures will be incorporated to promote abstinence (described below).

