At the start of each CREMA session, participants will be asked to stop using cannabis (if they are at the time), and provide ratings on craving, mood, and stress using a modified version of the Within Session Rating Scale (Childress et al., 1986). This visual analog scale is anchored with adjectival modifiers ("not at all, mildly, moderately, and extremely"). The scale includes items assessing anxiety, stress, irritability, and craving, and we have utilized it successfully in numerous previous studies. If the session is one of the two daily picture assessments, next a photograph (either stress-related or neutral) will be presented and the participant will be instructed to look at it carefully for 10 seconds. Each picture cue will appear only once during the study. An alarm will sound at the end of each trial, after which participants will complete a post-cue Within Session Rating Scale assessment, ratings of how carefully they looked at the photographs and their distraction level during each trial, and data on their cannabis use since last assessment. If the session is only collecting ambient stress and craving, immediately after the Within Session Rating Scale the participants will be asked to record data on cannabis use since the last assessment session. To encourage CREMA session completion, participants will be compensated \$5.00 for each completed session. Previous studies employing lower incentive strategies have reported 80-90% CREMA completion rates (Gass et al., 2012; Warthen et al., 2009), including in our previous SCOR (Wray et al., 2015); we have slightly increased compensation to maximize potential data collection over the 3-week period. CREMA sessions will begin on Day 2.

f. Progesterone Salivary Sample Collection. Participants will be instructed to collect a saliva sample each morning (1/2 hour after awakening). Samples will be dispensed into containers supplied by study staff and stored in participants' home freezers until bringing the samples to a subsequent study visit for analysis of progesterone levels. These daily home collection and storage procedures have been used in numerous previous studies with excellent participant adherence and sample quality (Edler et al., 2007; Klump et al., 2008). As discussed above in Preliminary Data, we successfully utilized a similar procedure in our last SCOR project. Participants will receive \$10 daily for collection of ovarian hormone salivary samples.

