
participants would provide 80% power or better to detect the proposed between sex and treatment comparisons noted in the primary study aims.

C.2.e. Design Considerations. **i) Choice of between vs. within participant design.** We considered implementation of a within-subject crossover design but opted instead for a between-subjects parallel-group comparison study for multiple reasons. Most notably, a within-subjects approach risks potential carryover effects between conditions, as well as potential dampening of cue reactivity and participant response fatigue over extended periods of testing across conditions. Additionally, withdrawal symptoms may not present consistently or reliably across multiple conditions in series without a lengthy/sustained return to *ad libitum* cannabis use between conditions. **ii) Choice of administration of progesterone during cannabis withdrawal.** Cannabis withdrawal is characterized by increased anxiety, irritability, craving, and physiological symptoms, which peak within the first 2-3 days of abstinence (Budhey et al., 2008). Acute cannabis withdrawal is therefore an ideal period to investigate potential therapeutic effects of progesterone on stress cue reactivity and craving. **iii) Focus on progesterone.** The proposed study focuses on progesterone because evidence suggests that estradiol may enhance drug reinforcement and cue-reactivity. In preclinical studies, estradiol has been shown to increase dopamine release in the ventral striatum in response to nicotine administration (Thompson et al., 1994), and facilitate methamphetamine-induced conditioned place preference (Chen et al., 2003) and cocaine self-administration (Lynch, 2008; Lynch et al., 2001). Clinical research on menstrual cycle phase has demonstrated greater smoking cue-elicited neural activity and craving response during the follicular phase (where estradiol dominates) compared to the luteal phase (Franklin et al., 2015; Mendrek et al., 2014). Likewise, women with a higher estradiol to progesterone ratio took more cigarette puffs and smoked more of a cigarette in a smoking topography study (Schiller et al., 2012). Furthermore, compared to men, women smokers in the follicular phase showed increased stress response and arousal while women in the luteal phase showed increased craving ([name] et al., 2015b). Together, evidence suggests that estradiol enhances drug reinforcement and cue-reactivity, and hence may contribute to the more deleterious outcomes observed in substance using women. Accordingly, we have focused this project on expanding knowledge about the treatment potential of progesterone (as characterized in the Significance above) by examining its effects on stress reactivity and substance use in persons with CUD. **iv) Male comparison group.** Apart from the obvious relevance of a male comparison group in studies of sex differences, there are empirical grounds for including men in proposed study. Sofuo glu et al., (2004) found that 2 oral doses of 200 mg progesterone significantly dampened cardiovascular responsiveness (diastolic BP) to iv cocaine in male, not female, cocaine users. Likewise, Fox et al., (2014) reported that exogenous progesterone vs. placebo attenuated cue-induced cocaine craving and cortisol responses in both men and women, suggesting that progesterone may also have some treatment potential for male cocaine users. Based on these and similar findings (Childs et al., 2010), we believe the proposed study's inclusion of both women and men with CUD will optimize our ability to identify therapeutic effects of progesterone that are either unique to one sex, or present in both.

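### The low-hormone window is guaranteed only for the Day 1 session: the Day 8 stress task falls after it in women, and the supplied model text names no cycle-day term

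*Combined protocol and SAP*

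**What the plan says.** C.2.c.3 states how women are scheduled: "menstrual history data will be used to schedule this session in the early follicular phase to standardize progesterone (or placebo) administration". The session meant is the Day 1 training visit, and no particular day within the window is required. The section defines the window as follows: "During the early follicular phase, defined as the first 7 days after the onset of menses, ovarian hormones are low and largely invariant". The same section gives the reason: "This is critical for two reasons; first, to minimize the interaction between endogenous and exogenous sex hormones". The second reason is comparability with men, because "progesterone levels in men are steady and similar to levels observed in women during most of the follicular phase". The approximate ceilings it gives for the window cover both hormones: 1.1 ng/ml for progesterone and 85 pg/ml for estradiol.

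The study days that follow are set elsewhere:
- Dosing (C.2.c.3.b): "Dosing will begin in the evening on study day 1", and "on day 8 the final dose will be taken at in the morning prior to completion of the laboratory stress task".
- Cue sessions (C.2.c.3.e): "CREMA sessions will begin on Day 2".
- TSST (C.2.c.4): Day 8, with rescheduling allowed to Day 9 and no later.

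In C.2.d.1, the Aim 1 model text names pre-cue stress and craving as covariates. The Aim 2 text names treatment, time, sex and the treatment-by-sex interaction. Neither names cycle day, and cycle day is not among the randomization strata in C.2.c.3.a. The menstrual history diary in C.2.c.2.a records the cycle before and during the study. C.2.d.1 refers to the Biostatistics Resource Core for the complete analysis plan.

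**The concern.** The standardisation is presented as essential, yet the scheduling rule secures it at the visit where medication is dispensed and not on the days when the outcomes are measured. Women may start anywhere in a 7-day range, so on any given study day they are spread over seven cycle days. Men have no corresponding source of variation.

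The protocol treats ovarian hormones as relevant to its outcomes. C.2.e (iii) argues that estradiol may enhance cue reactivity and cites "greater smoking cue-elicited neural activity and craving response during the follicular phase (where estradiol dominates) compared to the luteal phase". A.4 reports that high endogenous progesterone damped anxiety and craving responses to drug cues that followed a stressor. If hormone state varies among women at the assessments, the likely cost is residual variance in women and a less clean treatment-by-sex contrast, which is the contrast that sets the sample size in C.2.d.3. The diary already holds the information needed to account for part of that variation.

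**Working it through.** **1. Check of the day count.** C.2.c.5 allows up to $300 for cue sessions at $5 each: 300/5 = 60 sessions = 3 per day × 20 days, which is Days 2-21. It allows $140 for medication videos at $10 each: 140/10 = 14 doses = 1 (Day 1 evening) + 6 × 2 (Days 2-7) + 1 (Day 8 morning). Both agree with the stated schedule, so the on-treatment cue days before the TSST are Days 2-7, six days.

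**2. Cycle day on each study day.** Let c be the cycle day of the Day 1 session, with onset of menses as cycle day 1, so c = 1 to 7. Study day d is then cycle day c + d − 1. A day is outside the window if this exceeds 7.

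| Start day c | Cycle days on Days 2-7 | Cue days outside (of 6) | Cycle day at Day 8 | at Day 9 |
|---|---|---|---|---|
| 1 | 2-7 | 0 | 8 | 9 |
| 2 | 3-8 | 1 | 9 | 10 |
| 3 | 4-9 | 2 | 10 | 11 |
| 4 | 5-10 | 3 | 11 | 12 |
| 5 | 6-11 | 4 | 12 | 13 |
| 6 | 7-12 | 5 | 13 | 14 |
| 7 | 8-13 | 6 | 14 | 15 |

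The TSST is outside for 7 of 7 start days, whatever their distribution. If onset is counted as day 0, a woman seen on the day of onset has Day 8 on day 7, so 7 of 8 start days are outside.

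**3. Average share of cue days outside.** The documents give no distribution of start days, so each line is an assumption (uniform over the range shown):
- c = 1-7: 21/42 = 50%
- c = 1-3: 3/18 = 17%
- c = 1-5: 10/30 = 33%
- c = 2-7: 21/36 = 58%
- c = 3-7: 20/30 = 67%
- onset as day 0, c = 0-7: 21/48 = 44%

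**4. Women reaching ovulation.** Assume ovulation 14 days before the next menses, start days uniform over 1-7, and cycle length L uniform over the 25-35 days that eligibility allows. That gives 7 × 11 = 77 combinations.
- Day 8 on or after ovulation, c + 7 ≥ L − 14: 1 + 2 + 3 + 4 = 10 (c = 4 to 7), so 10/77 = 13%.
- Day 8 strictly after ovulation: 1 + 2 + 3 = 6 (c = 5 to 7), so 6/77 = 8%.
- In a 25-day cycle, 4 of 7 start days put Day 8 on or after ovulation and 3 of 7 strictly after. In cycles of 28 to 35 days none is strictly after.
- Cue days (Days 2-7; 77 × 6 = 462): 10/462 = 2.2% on or after, 4/462 = 0.9% strictly after.

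**5. Chance imbalance between arms.** With c uniform on 1-7 its variance is (7² − 1)/12 = 4, so the SD is 2 days. With the 32 women per arm of C.2.d.3, the standard error of the difference in mean start day is 2 × √(2/32) = 0.5 day.

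**The case against.** Several objections stand and limit the point.

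- **No passage says that the TSST lies in the first 7 days.** C.2.c.3 schedules only the first session there, and C.2.c.3.b makes no cycle-day claim about this trial's stress task. A reader might infer an outright contradiction; the text supports only a rationale that reaches further than the schedule secures.
- **Leaving the window is not leaving the low-progesterone state.** The match with men rests on most of the follicular phase, and C.1.f describes the group's own data as showing low, stable progesterone for most of the first half of the cycle. Mainly the estradiol part of the claim is exposed, plus short cycles. For the Aim 1 cue days, a rise in progesterone after ovulation is negligible under the assumptions in step 4.
- **The supporting evidence is indirect.** The comparison cited in C.2.e (iii) is follicular against luteal, in smokers. It does not show that reactivity differs between cycle days 1-7 and 8-14.
- **The complete analysis plan is elsewhere.** The absence of a cycle-day term can be stated only for the supplied text, which also allows unspecified relevant interactions.
- **Randomization balances cycle day between arms on average.** The size of any variance gain is unknown.

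These narrow the point without removing it. The protocol claims that both hormones are low and largely invariant only for the first 7 days, and the TSST lies beyond them.

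**Conclusion.** The concern holds in limited form. The window is guaranteed only for the Day 1 session. With onset as cycle day 1, every woman's TSST is on cycle day 8-14 (9-15 if moved to Day 9), and this needs no assumption about start days. The cue-day average and the 8%-13% of TSSTs after, or on or after, ovulation do rest on the assumptions stated in the working.

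Three stronger readings are tempting and are not supported. The window does not cover Day 1 alone: a woman who starts on cycle day 1 has all six cue days inside it. It cannot be said that most Aim 1 data lie outside, because the share depends on an unknown start-day distribution. Nor is systematic treatment bias expected: by chance the arms would typically differ by about half a cycle day. What is at stake is precision in women and the standardisation of the treatment-by-sex contrast. The change is worth making because the covariate is already collected, not because the planned analysis is invalid.

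**What to change.** 1. **Reconcile the text.** Bring the rationale in C.2.c.3 into line with the dosing days in C.2.c.3.b, the cue days in C.2.c.3.e and the TSST days in C.2.c.4, so that it is clear which study days the low-hormone claim covers. State whether onset counts as day 0 or day 1. This is a change of wording and requires no change of dose or schedule.

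2. **Prespecify one covariate.** Add cycle day at the Day 1 session, from the menstrual diary, to the Aim 1 and Aim 2 models. Centre it among women and nest it within women (men take the value 0). It is fixed before dosing, so treatment cannot affect it. Cycle day on Day 8 is c + 7, so at a Day 8 TSST the covariate carries the same information as cycle day itself. If the Biostatistics Resource Core plan already contains such a term, citing it is enough.

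3. **Avoid two alternatives.** An indicator for days beyond the window is constant in women at the TSST (and aliased with sex if men are coded 0), and in Aim 1 it switches on as days of abstinence accumulate. On-treatment salivary progesterone is changed by treatment and should not be the adjuster.

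Cost: wording, plus about one degree of freedom per model. The covariate can improve precision among women; it cannot by itself make women and men hormonally comparable.

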a. Medication Randomization. Randomization will be done by the MUSC Investigational Drug Service, who will keep a record of the blind and be available should unblinding be required. Randomization will be stratified on the presence/absence of nicotine use as well as the presence/absence of comorbid anxiety disorders (as these disorders can influence stress reactivity).

b. Micronized progesterone (Prometrium; 200mg): Progesterone is a hormone released mainly during the luteal phase of the menstrual cycle and pregnancy, and has been used for over 50 years in the treatment of various disorders including ovarian failure, premenstrual symptoms, amenorrhea, dysfunctional uterine bleeding, menopausal symptoms and for contraception (de Lignieres, 1999; Simon, 1995). Because it is poorly absorbed and has extensive first pass metabolism, several synthetic progesterone derivatives have been synthesized and marketed. However, these synthetic progesterone derivatives have additional androgenic, corticosteroid and

anabolic effects and have been associated with unfavorable side effects including fluid retention, androgenic effects (e.g., unwanted hair growth and acne) and alterations in lipid profile (Goodman, Gilman, Hardman, Gilman, & Limbird, 1996). Consequently, micronized progesterone formulations that can be taken orally have been developed to overcome the poor absorption of progesterone and the unfavorable side effects of synthetic progesterones (McAuley, Kroboth, & Kroboth, 1996; Simon, 1995). The safety, tolerability and efficacy of micronized progesterone have been demonstrated in multiple studies. Acute effects of micronized progesterone on physiological, performance and subjective measures have been investigated over a wide dose range, from 200 to 2,000 mg/day (Freeman, Rickels, Sondheimer, & Polansky, 1995; Gron, Friess, Herpers, & Rupprecht, 1997; Schweizer, Case, Garcia-Espana, Greenblatt, & Rickels, 1995). Micronized progesterone provides a specific pharmacological tool to investigate the effects of this hormone, devoid of the additional pharmacological effects of synthetic progesterone derivatives.

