Data Management and Reduction: All paper-based assessments (other than laboratory reports) will be entered into REDCap, a secure, web-based application designed exclusively to support data capture for research studies. REDCap provides an intuitive interface for data entry (with data validation), audit trails for tracking data manipulation, and automated export procedures for data downloading to statistical packages such as SPSS and SAS. Quarterly database management and data integrity audits will be conducted.

C.2.d. Statistical Considerations

C.2.d.1. **Statistics and Data Analysis** (complete data analytic plan is provided in Biostatistics Resource Core)

Aim 1: Examine the impact of exogenous progesterone on stress cue reactivity and cannabis craving and withdrawal symptoms during a period of cannabis abstinence in the natural environment.

The primary measures of interest are stress and craving ratings in response to stress-related cues using Cue Reactivity Ecological Momentary Assessment (CREMA) in heavy cannabis using women and men. Hypothesis 1: Compared to placebo, progesterone will attenuate reactivity to stress cues presented in the natural environment among women vs. men with CUD. Hypothesis 2: Compared to placebo, progesterone will attenuate cannabis craving and withdrawal symptoms among women vs. men with CUD. To assess these hypotheses multilevel generalized linear mixed effects models with repeated measures (GLMMs) will be developed using CREMA session response data from the 1-week period during active medication administration. Pre-cue stress and craving rating will be centered and used as a time varying covariate in all analysis. Least squares means and associated standard errors will be used for post-hoc comparisons of cue response and CWS scores between treatment group assignments globally as well as time-specific (AM, PM) treatment group differences. Least squares means and associated standard errors will also be used for post-hoc comparisons of craving and stress response between women and men over time. Relevant interactions will be assessed in the models.

Aim 2: Examine the impact of exogenous progesterone on stress cue reactivity during a laboratory stressor task.

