Following the initial 7-day active exogenous progesterone treatment period, participants will return for a laboratory-based stressor a session. The primary study outcomes of interest in Aim 2 are the differential craving, stress and anxiety responses of progesterone- vs. placebo-treated participants in response to the psychosocial stressor (TSST). Hypothesis 1: Compared to placebo, progesterone will attenuate stress cue reactivity during a human laboratory stress paradigm among women but not men with CUD. Immediately prior to and following the TSST (baseline, +0, +5, +30, and +60 minutes), self-reported measures of stress and craving will be collected. To assess the effect of exogenous progesterone administration on stress and craving response to the TSST, linear mixed effects models will be developed to assess differential treatment responses over time. The primary independent variable of interest will be randomized treatment assignment (progesterone vs. placebo). In addition to overall treatment differences, least squares means and associated standard errors will be used for post-hoc

comparisons between treatment groups at each post-cue time point. Additionally, sex will be added to the model and differential effect of progesterone will be assessed using an interaction term. When significant, stratified treatment effects will be compared and presented across females and males.

Aim 3: Evaluate stress, sex, and endogenous progesterone influences on cannabis craving and use.

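### Randomisation is stratified by nicotine use and comorbid anxiety disorder, but the described Aim 1 and Aim 2 models name neither; adding both would sharpen the overall and time-point comparisons if they are prognostic.

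*Combined protocol and SAP*

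**What the plan says.** Section C.2.c.3 a (Medication Randomization): "Randomization will be stratified on the presence/absence of nicotine use as well as the presence/absence of comorbid anxiety disorders". The reason given for the anxiety factor is "as these disorders can influence stress reactivity". No reason is given for nicotine use.

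Section C.2.d.1 begins by noting that the "complete data analytic plan is provided in Biostatistics Resource Core". It then describes the models:

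- **Aim 1.** "Pre-cue stress and craving rating will be centered and used as a time varying covariate in all analysis". Least squares means serve for "post-hoc comparisons of cue response and CWS scores between treatment group assignments globally" and for AM and PM comparisons. Interactions judged relevant are to be assessed but are not listed.
- **Aim 2.** "linear mixed effects models will be developed to assess differential treatment responses over time". Treatment is the main independent variable. "In addition to overall treatment differences, least squares means and associated standard errors will be used" for "comparisons between treatment groups at each post-cue time point". Sex and its interaction with treatment are then added.

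Neither description mentions nicotine use or anxiety disorder as a model term.

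**The concern.** Stratified randomisation balances the arms on the chosen factors, so the true sampling variation of the treatment difference no longer contains the variation due to them. A model that omits the factors still counts that variation as residual error. Its standard error is then too large, and the test rejects less often than its nominal level. The estimate stays unbiased, and because C.2.d.3 assumes a Gaussian outcome, adjustment does not change what is being estimated.

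What is at stake is precision in comparisons of response level: the global cue-response and withdrawal comparisons in Aim 1, the overall and time-point comparisons in Aim 2, and the level version of the treatment by sex interaction on which the trial is powered.

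**Working it through.** **Inputs from the protocol.** C.2.d.3: treatment by sex difference 3.1, SD 4.7, d=0.67, 32 participants per sex-by-arm cell (128 in total), 5% type 1 error, 10% attrition. C.2.c.3 e: one stress cue a day, with sessions starting on Day 2. C.2.d.1: five assessment times in Aim 2.

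**Assumed, because the protocol does not give them.** The share R² of variance explained by the two factors, their prevalence, the block size, the intraclass correlation (ICC) and a two-sided test.

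**1. The plan's own figure.** Noncentrality = 0.67 × √(32/2) = 2.68. Two-sided power at 5% is 76.4% by the normal approximation and 75.8% by noncentral t, not the stated 80%. Reaching 80% by the normal approximation takes 35 per cell. That shortfall is a separate matter; 75.8% is simply the baseline below.

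**2. Level comparisons, one mean per person.** Residual SD is multiplied by √(1−R²).

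| Assumed R² | SE ratio | Fall in SE | Interaction power, 32 per cell (noncentral t) |
|---|---|---|---|
| 0 | 1.000 | 0% | 75.8% |
| 0.05 | 0.975 | 2.5% | 77.9% |
| 0.10 | 0.949 | 5.1% | 80.0% |
| 0.20 | 0.894 | 10.6% | 84.4% |

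**3. Type I error of the overall treatment test.** Simulation with 128 people, unit SD, blocks of 4 in the 4 strata, 50% nicotine use, 25% anxiety disorder and 8000 trials per setting:

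| R² | Without strata: model SE / true SD / type I error | With strata: model SE / type I error |
|---|---|---|
| 0 | 0.176 / 0.177 / 5.0% | 0.176 / 5.0% |
| 0.10 | 0.176 / 0.166 / 3.7% | 0.167 / 4.6% |
| 0.20 | 0.177 / 0.158 / 2.6% | 0.158 / 4.6% |

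A second simulation (64 men and 64 women, 30% anxiety disorder, 5000 trials) gave 3.7% and 3.3% without the strata at R² 0.10 and 0.20. Its level treatment by sex power, without and then with the strata, was 75.2% and 74.4% at R² 0, 75.7% and 78.7% at 0.10, and 75.5% and 83.7% at 0.20. The drop of 0.8 points at R² 0 is the price if neither factor matters.

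**4. Aim 2, five times, random intercept, between- and within-person variance both 1 (assumed).** If the strata explain a share r of the between-person variance, the average over time has variance proportional to (1−r) + 1/5, and a single time point (1−r) + 1. For r = 0.10:

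- average: √(1.1/1.2) = 0.957, a fall of 4.3%
- single time point: √(1.9/2) = 0.975, a fall of 2.5%

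Generalised least squares standard errors for treatment by sex, which also carry the small cost of strata not exactly balanced within sex-by-arm cells, fall by 3.5% and 8.0% (average) and 2.1% and 4.7% (single time point) at r = 0.10 and 0.20. For treatment by time and treatment by sex by time the change is 0.0%: a factor that is constant within a person drops out of that person's differences. The same holds for treatment by cue type.

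**5. Aim 1.** Days 2 to 7 give 6 stress cues. The between-person share of a 6-cue mean is ICC / (ICC + (1−ICC)/6): 0.60 at ICC 0.2 and 0.857 at ICC 0.5. With r = 0.10 or 0.20, effective R² is 0.06 or 0.12 at ICC 0.2, and 0.086 or 0.171 at ICC 0.5. The standard error falls by 3.0 or 6.2%, and by 4.4 or 9.0%. With 63 evaluable men and 63 women (70 of each less 10%, assumed), difference 3.1 and cell SD 3.35, power is 73.1% without the strata and 75.7 to 80.8% with them. If the pre-cue rating already absorbs half of what the strata explain (assumed), the falls are 1.5 to 4.4% and power is 74.4 to 76.9%.

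**The case against.** The strongest reply is that C.2.d.1 is a summary. The full plan is elsewhere, the models are still to be developed, and a term missing from a summary may be present in the plan. This stands as a limit on the claim: a reader of this protocol cannot tell, and the remedy may shrink to one sentence.

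The gain may also be small. Only anxiety disorder has a stated reason, and that reason concerns stress reactivity, not craving or withdrawal. If anxiety alone carried the effect at 30% prevalence, R² = 0.10 would need a mean shift of √(0.10/0.21) = 0.69 SD. That is about the progesterone effect in women (d=0.71) from the trial cited in C.2.d.3. R² = 0.20 would need 0.98 SD. Smaller shifts suffice if nicotine use also matters, but the protocol gives no effect for it. The lower end of the range is therefore the safer guide, and "Pre-cue stress and craving rating will be centered and used as a time varying covariate in all analysis" takes up part of the gain in Aim 1 cue responses. It may take up less for the Cannabis Withdrawal Scale, which comes from the adherence survey (C.2.c.3 g) and has no cue session attached. The Aim 2 description names no baseline covariate.

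Finally, contrasts over time or between cue types gain nothing. That is correct, but both aims also plan level comparisons.

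**Conclusion.** The point holds as a should-fix matter of precision, with medium confidence. The described models leave out both factors used to stratify randomisation. There is no bias, and the false-positive rate is not raised. If the factors are prognostic, the overall treatment test is conservative (type I error roughly 2.6 to 3.7% at assumed R² of 0.10 to 0.20), and the level treatment by sex comparison gives up some power: about 2 points at R² 0.05, 4 at 0.10 and 9 at 0.20 at the planned 32 per cell. In Aim 1, with the pre-cue rating absorbing half, the gain is about 1 to 4 points over 73%. Every size rests on assumed R², prevalence and variance components. The direction does not, and at R² = 0 the gain is nil with a small loss. The case for nicotine use rests on its being a stratification factor, not on any effect stated in the protocol.

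**What to change.** In C.2.d.1, add nicotine use (yes/no) and comorbid anxiety disorder (yes/no), as recorded at randomisation, as fixed effects in the Aim 1 and Aim 2 models, alongside treatment, sex and treatment by sex. If the Biostatistics Resource Core plan already includes them, say so there.

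The cost is two model terms. Both values are known at randomisation, so no new data are needed and the allocation list does not change. If neither factor is prognostic, the level treatment by sex test loses about 0.5 to 0.8 power points; treatment by time contrasts lose nothing.
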